**Same shell as Table 14.3.5.1.1**

**Programming note:** Update footnote to SOURCE: Listing 16.2.8.1.2

Table 14.3.5.2.2  
Shift from Baseline in Serum Chemistry Laboratory Results by Study Visit  
Safety Population

**Same shell as Table 14.5.1.2**

**Programming note:** Update footnote to SOURCE: Listing 16.2.8.1.2

Table 14.3.5.3.1  
Summary of Quantitative Urinalysis Laboratory Results by Study Visit  
Safety Population

**Same shell as Table 14.3.5.1.1**

**Programming note:** Update footnote to SOURCE: Listing 16.2.8.1.3

Table 14.3.5.3.2  
Shift from Baseline in Quantitative Urinalysis Laboratory Results by Study Visit  
Safety Population

**Same shell as Table 14.3.5.1.2**

**Programming note:** Update footnote to SOURCE: Listing 16.2.8.1.3

Table 14.3.5.3.3  
Summary of Qualitative Urinalysis Laboratory Results by Study Visit  
Safety Population

Parameter: XXXXXXXX	Cohort-1 (N=XX) n (%)	Cohort-2 (N=XX) n (%)	Overall (N=XX) n (%)
Study Visit Category			
Screening			
Category 1	XX (XX.X%)	XX (XX.X%)	XX (XX.X%)
Category 2	XX (XX.X%)	XX (XX.X%)	XX (XX.X%)
Category 3	XX (XX.X%)	XX (XX.X%)	XX (XX.X%)
Baseline [1]			
Category 1	XX (XX.X%)	XX (XX.X%)	XX (XX.X%)
Category 2	XX (XX.X%)	XX (XX.X%)	XX (XX.X%)
Category 3	XX (XX.X%)	XX (XX.X%)	XX (XX.X%)
Day 1			
Category 1	XX (XX.X%)	XX (XX.X%)	XX (XX.X%)
Category 2	XX (XX.X%)	XX (XX.X%)	XX (XX.X%)
Category 3	XX (XX.X%)	XX (XX.X%)	XX (XX.X%)
Day 7			
Category 1	XX (XX.X%)	XX (XX.X%)	XX (XX.X%)
Category 2	XX (XX.X%)	XX (XX.X%)	XX (XX.X%)
Category 3	XX (XX.X%)	XX (XX.X%)	XX (XX.X%)
Day 14			
Category 1	XX (XX.X%)	XX (XX.X%)	XX (XX.X%)
Category 2	XX (XX.X%)	XX (XX.X%)	XX (XX.X%)
Category 3	XX (XX.X%)	XX (XX.X%)	XX (XX.X%)
Day 21			
Category 1	XX (XX.X%)	XX (XX.X%)	XX (XX.X%)
Category 2	XX (XX.X%)	XX (XX.X%)	XX (XX.X%)
Category 3	XX (XX.X%)	XX (XX.X%)	XX (XX.X%)

Note: Percentages are n/Number of subjects in the Safety Population and respective Protocol Amendment\*100.

[1] The baseline value for each variable is the last observation recorded prior to the first dose of treatment.

SOURCE: Listing 16.2.8.1.3

**Programming Note:** Continue all parameters. Sort alphabetically by parameter.

Table 14.3.5.4.1  
Summary of Quantitative Biomarker Panel for Renal Tubular Injury Results by Study Visit  
Safety Population

Parameter: uCreatine (uCr); CAD-1883 Treatment 300mg BID		Cohort-1 (N=XX)		Cohort-2 (N=XX)		Overall (N=XX)	
Study Visit Statistic	Results (Measured) ng/mL	Results (Measured) ng/mL	Results (Normalized) ng/mg Cr	Results (Normalized) ng/mg Cr	Results (Normalized) ng/mg Cr	Results (Normalized) ng/mg Cr	
Baseline [1]							
n	xx	xx	xx	xx	xx	xx	
Mean (SD)	xxx.x (xxx.xx)	xxx.x (xxx.xx)	xxx.x (xxx.xx)	xxx.x (xxx.xx)	xxx.x (xxx.xx)	xxx.x (xxx.xx)	
Median	xxx.x	xxx.x	xxx.x	xxx.x	xxx.x	xxx.x	
Min, Max	x, xxx	x, xxx	x, xxx	x, xxx	x, xxx	x, xxx	
Day 1							
n	xx	xx	xx	xx	xx	xx	
Mean (SD)	xxx.x (xxx.xx)	xxx.x (xxx.xx)	xxx.x (xxx.xx)	xxx.x (xxx.xx)	xxx.x (xxx.xx)	xxx.x (xxx.xx)	
Median	xxx.x	xxx.x	xxx.x	xxx.x	xxx.x	xxx.x	
Min, Max	x, xxx	x, xxx	x, xxx	x, xxx	x, xxx	x, xxx	
Fold Change from Baseline to Day 1							
n	-	-	xx	xx	xx	xx	
Mean (SD)	-	-	xx.xxx (xx.xxxx)	xx.xxx (xx.xxxx)	xx.xxx (xx.xxxx)	xx.xxx (xx.xxxx)	
Median	-	-	x.xxx	x.xxx	x.xxx	x.xxx	
Min, Max	-	-	x.xx, xx.xx	x.xx, xx.xx	x.xx, xx.xx	x.xx, xx.xx	

BID=Twice a day, SD=Standard Deviation, Min=Minimum, Max=Maximum.

Note: The normalized concentration at a given time point is calculated as the concentration at that time point divided by the concentration of uCreatinine (mg/dL) at the same time point. Fold Change from Baseline at a given time point is calculated as the normalized concentration at the time point divided by the normalized concentration at baseline.

Commercially Confidential Information

[1] The baseline value for each measure is the last observation recorded prior to the first dose of treatment.

SOURCE: Listing 16.2.8.1.4.

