#### **3.2. Sample Size and Power**

Up to 30 subjects will be enrolled. No formal statistical power analysis was conducted.

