## 4. Statistical Analysis and Reporting

### 4.1. Introduction

Data processing, tabulation of descriptive statistics, calculation of inferential statistics, and graphical representations will be performed primarily using SAS (release 9.4 or higher).

Commercially Confidential Information If the use of other software is warranted, the final statistical methodology report will detail what software was used for what purposes.

Continuous (quantitative) variable summaries will include the number of subjects (n) with non-missing values, mean, standard deviation (SD), median, minimum, and maximum.

Categorical (qualitative) variable summaries will include the frequency and percentage of subjects who are in the particular category for each possible value. In general, the denominator for the percentage calculation will be based upon the total number of subjects in the study population, unless otherwise specified. The denominator for by-visit displays will be the number of subjects in the relevant study population with non-missing data at each visit. If there is any missing value for a categorical analysis, a “Missing” category will be displayed as the last category in the table for the variable.

For weight, height, CCI one decimal place will be used for all summary statistics. For all other summaries, the minimum and maximum will be reported with the same degree of precision (i.e., the same number of decimal places) as the observed data. Measures of location (mean and median) and confidence interval boundaries will be reported to 1 degree of precision more than the observed data, up to 3 decimal places. Measures of spread (SD) will be reported to 2 degrees of precision more than the observed data, up to 3 decimal places.

Percentages will be presented to 1 decimal place, unless otherwise specified. Percentages equaling 0 or 100 will be displayed with no decimal places or percentage symbols.

Fractional numeric values will be presented with a zero to the left of the decimal point (for example, 0.12 – 0.30).

Unless otherwise indicated, all statistical tests will be conducted at the 0.05 significance level using 2-tailed tests, and *P* values will be reported. Corresponding 95% confidence intervals (CIs) will be presented for statistical tests, where applicable.

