**Programming note:**

Parameters are uCreatine (uCr), uClusterin (uCLU) , uCystatin-C (uCysC), uKidney Injury Molecule-1 (uKIM-1), u N-Acetyl-beta-D-Glucosaminidase (uNAG), Neutrophil Gelatinase-Associated Lipocalin (uNGAL) and uOsteopontin (uOPN).

Keep the decimal places as exactly the same as what is shown in this table shells

Exten the table for visits Day 7, 14 and 21.

Table 14.3.5.4.2

Geometric Mean (GM) Composite Measure (CM) on Quantitative Biomarker Panel for Renal Tubular Injury Results by Study Visit  
Safety Population

Visit	Number of Subjects (N=xx)	GM CM
Baseline	xx	x.xx
Day 1	xx	x.xx
Day 7	xx	x.xx
Day 14	xx	x.xx
Day 21	xx	x.xx

GM CM = Geometric Mean (GM) Composite Measure (CM)

***Programming note:*** Update footnote to SOURCE: Listing 16.2.8.1.4

Table 14.3.6.1.1  
Summary of Vital Signs by Study Visit  
Safety Population

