**Same shell as Figure 14.2.1.1.4**

Y-axis: Central Score  
X-axis: Local Score

Programming notes: A separate graph will be produced for each study visit. Update the footnote to read: TETRAS-PS Upper Limb Tremor (Item 4) Total score is derived as the sum of the 6 item 4 scores (forward outstretched postural tremor, lateral “wing beating” postural tremor, and kinetic tremor scores) from both sides of the body, with a maximum total score of 24. Kinesia Upper Limb Tremor score is derived as the sum of the scores from the extended arms posture, wing-beating posture, and kinetic “finger-to-chin” wearable sensor maneuvers from both sides of the body, with a maximum total score of 24.

[figure not shown]
Reference Table: 14.2.6.1

SOURCE: Listings 16.2.6.1.1 and 16.2.6.6.1

Commercially Confidential Information

Commercially Confidential Information

Figure 14.5  
Geometric Mean (GM) Composite Measure (CM) of Kidney Injury Biomarkers by Study Visit  
Safety Population

Programming note: Remove "GM CM of CAD1883-201 subjects as of Fri, 5/17/2019" from the graph. The threshold values need to be updated per the user guide (Threshold=1.18 with n=20).

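### In SAP Table 14.3.5.4.1 the arithmetic mean of single-marker renal fold changes is above 1 in expectation when nothing has changed; a geometric mean should replace or join it

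*SAP*

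**What the plan says.** SAP Section 9.7 divides each urinary marker by urinary creatinine from the same timepoint, then divides that normalised value by its baseline counterpart. The note under Table 14.3.5.4.1 (SAP Section 14.2) repeats this: the fold change "is calculated as the normalized concentration at the time point divided by the normalized concentration at baseline".

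In the shell, the block headed "Fold Change from Baseline to Day 1" has rows for n, mean (SD), median and min/max. A programming note extends the table to Days 7, 14 and 21. These rows follow SAP Section 4.1, where continuous variables are summarised by the count of non-missing values, "mean, standard deviation (SD), median, minimum, and maximum". For single-marker fold changes, no visible text mentions a geometric mean, a geometric coefficient of variation or a log transformation.

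The composite is treated differently. Table 14.3.5.4.2 is titled "Geometric Mean (GM) Composite Measure (CM) on Quantitative Biomarker Panel for Renal Tubular Injury Results by Study Visit". Figure 14.5 plots the same geometric-mean composite, with a programming note giving "Threshold=1.18 with n=20".

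On design, SAP Section 3.5 describes one treatment group without randomisation, and SAP Section 3.2 says "Up to 30 subjects will be enrolled". Protocol Section 6.1.2 takes the baseline marker level from a urine sample at the Baseline/Pre-dose visit.

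Text is redacted after the definitions in Section 9.7 and in the table note. The shell's statistic rows are visible.

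**The concern.** A fold change is a ratio, so its scale is asymmetric: a rise can add any amount above 1, while a fall can subtract at most 1. Averaging such ratios arithmetically gives rises more weight than equal proportional falls. One subject who doubles and one who halves should average to no change, but their arithmetic mean is 1.25.

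Readers will compare these means with 1. In a controlled trial the comparison arm would carry a similar upward shift and the eye would correct for it. Here both cohort columns receive the study drug, so nothing in the table shows what a no-change mean looks like. Safety is the primary objective and renal tubular injury has its own panel, tables and figure, so a mean row that drifts upward from noise alone invites over-reading.

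**Working it through.** **Inputs.** The quantity is the per-subject ratio defined in SAP Section 9.7 and the note to Table 14.3.5.4.1. The statistic is the mean (SD) row of that shell, read with SAP Section 4.1. The maximum sample size is 30 (SAP Section 3.2). The documents give no variability for any marker, so every SD or CV below is assumed. The plan states no figure for this row to reproduce.

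**Step 1: direction, without a distribution.** Let X be the visit value and Y the baseline value for one subject, both positive. If nothing has changed they are exchangeable, so E[X/Y] = E[Y/X]. For any positive ratio r, (r + 1/r)/2 ≥ 1, with equality only at r = 1. Hence E[X/Y] > 1 unless X and Y are always equal. The geometric mean of the ratio is 1, because E[log X − log Y] = 0. With one doubling and one halving, (2 + 0.5)/2 = 1.25, while √(2 × 0.5) = 1.00.

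**Step 2: size, by SD of the log ratio.** If the log ratio is normal with mean 0 and SD s, the expected arithmetic mean is exp(s²/2), and the median and geometric mean are 1.

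- s = 0.3: exp(0.045) = 1.046
- s = 0.5: exp(0.125) = 1.133
- s = 0.6: exp(0.180) = 1.197
- s = 0.7: exp(0.245) = 1.278

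This expectation does not depend on the number of subjects. A larger sample does not remove the bias.

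**Step 3: size, by within-subject CV.** Suppose baseline and visit values are independent within a subject, each log-normal with coefficient of variation CV. Then s² = 2 ln(1 + CV²), so exp(s²/2) = 1 + CV². A simulation of 40,000 no-change trials with 30 subjects gave:

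| CV | s | Expected arithmetic mean | Trials with arithmetic mean above 1 | Trials with geometric mean above 1 |
|---|---|---|---|---|
| 0.2 | 0.280 | 1.04 | 77.0% | 50.4% |
| 0.3 | 0.415 | 1.09 | 85.6% | 50.3% |
| 0.4 | 0.545 | 1.16 | 91.0% | 50.2% |
| 0.5 | 0.668 | 1.25 | 94.5% | 50.1% |

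The sample median centred on 1.00 throughout. With 20 subjects the arithmetic mean exceeded 1 in 71.5% of trials at CV 0.2 and 90.2% at CV 0.5.

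**Step 4: which rows are affected.** Section 9.7 and the programming note name seven parameters including creatinine. Creatinine divided by itself is 1 at every timepoint, so its fold change is 1 by construction. The point concerns the other six markers.

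**The case against.** The strongest reply is that the block already contains the remedy. The median sits directly below the mean and centres on 1 under the same model, so a mean of 1.13 beside a median of 1.00 shows a skewed ratio and would not be read as a renal signal. Individual values are listed, the table is descriptive with no visible test or decision rule, and the rows follow the SAP-wide convention. The size rests on an assumed SD, and at SD 0.3 the excess is only 5%. All of this stands and makes the point small. It does not make the mean row a good summary of a ratio, and the median has no interval beside it.

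It can also be said that the mean is not labelled arithmetic and that redacted text might qualify it. The plain reading is arithmetic: Section 4.1 pairs the mean with an SD, the SAP writes geometric mean where it intends one, and the visible rows contain none.

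A reader might infer four stronger things that the documents do not support:

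- **That noise alone could carry a marker to the 1.18 threshold.** The threshold belongs to the composite in Figure 14.5, which is already a geometric mean. No visible text applies it to a single marker.
- **That the table could hide which marker moves the composite.** No calculation shows this, and each marker's median is displayed.
- **That the mean must exceed 1 when nothing changes.** This holds in expectation only. At CV 0.2 with 30 subjects, about 23% of no-change trials (100% − 77%) do not exceed 1.
- **That the two tables contradict each other.** They report different quantities, and the composite's formula cannot be checked in the visible text. What can be said is that the averages are on different scales.

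**Conclusion.** The point holds as a modest improvement to one row of a descriptive table. For the six markers other than creatinine, the arithmetic mean fold change is above 1 in expectation when there is within-subject variation and no systematic change. The direction needs only exchangeable baseline and visit values. The size, 1.05 to 1.28, rests on a log-normal model and an assumed log-scale SD of 0.3 to 0.7, and real markers may lie outside that range. The absence of a control column is what makes the row easy to misread in this trial. The median, the composite and the comparison of the composite with its threshold are unaffected.

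**What to change.** In the fold-change rows of Table 14.3.5.4.1 at Days 1, 7, 14 and 21, for the six markers other than creatinine, replace the mean (SD) with the geometric mean and its 95% confidence interval, or add them beside it. Keep n, the median and the range. Take the natural log of each subject's ratio, compute the mean m and SD s over the n subjects, and report exp(m) with limits exp(m ± t × s/√n), where t is the 97.5th percentile on n − 1 degrees of freedom. Single markers and the composite are then averaged on the same scale.

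Add one sentence to SAP Section 9.7 stating this exception to Section 4.1, and give the display format, because the programming note fixes the decimals as shown in the shell. Logs need positive values, so also state how results below the limit of quantification enter the ratio; the visible text gives no rule for these markers.

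The cost is one shell edit and a few lines of code, with no new data and no change to study conduct.

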## **9.7 Kidney safety Composite Measure Biomarker**

The following 6 kidney safety composite measure biomarkers were tested using urine sample: uCreatine (uCr), uClusterin (uCLU) , uCystatin-C (uCysC), uKidney Injury Molecule-1 (uKIM-1), u N-Acetyl-beta-D-Glucosaminidase (uNAG), Neutrophil Gelatinase-Associated Lipocalin (uNGAL) and uOsteopontin (uOPN). Measured concentration is first normalized by dividing it by the concentration of uCR at the same timepoint. The fold change from baseline at a given timepoint is then calculated using the normalized concentration at a time point divided by the normalized concentration at baseline. For example, the normalized uCysC concentration at a given timepoint is calculated as the concentration of CysC at that timepoint divided by the concentration of uCr at the same timepoint. The uCysC fold change from baseline at a given timepoint is calculated as the normalized CysC concentration at a given timepoint divided by the normalized uCysC concentration at baseline. Similar calculations apply to other composite measures.

Commercially Confidential Information

Commercially Confidential Information

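### In SAP Table 14.3.5.4.1, normalised renal biomarkers come out 100 times too low for their ng/mg Cr label if the note is followed literally, and creatinine is normalised to itself

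*SAP*

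**What the plan says.** The calculation rule appears in two places. SAP 9.7 gives it without units: "Measured concentration is first normalized by dividing it by the concentration of uCR at the same timepoint". The note under the shell for Table 14.3.5.4.1 (SAP 14.2) gives it with a unit for the divisor: the concentration is "divided by the concentration of uCreatinine (mg/dL) at the same time point". The column headings in that shell are "Results (Measured) ng/mL" and "Results (Normalized) ng/mg Cr". Neither place states a conversion factor. Both then define fold change as the normalised value at a visit over the normalised value at baseline.

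On which analytes are biomarkers, SAP 9.7 opens with "The following 6 kidney safety composite measure biomarkers were tested using urine sample" and then names seven: uCr, uCLU, uCysC, uKIM-1, uNAG, uNGAL and uOPN. The first of these is also the divisor. The programming note under the table repeats all seven as parameters, and the shell itself is drawn for creatinine: "Parameter: uCreatine (uCr); CAD-1883 Treatment 300mg BID". The lists, the shell and the programming note call the analyte creatine; the table note calls it creatinine.

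The programming note also tells the programmer to keep the decimal places exactly as shown. For the concentration rows these are one decimal for the mean and median and none for the minimum and maximum.

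**The concern.** A concentration in ng/mL divided by one in mg/dL is not in ng/mg. The note and the column heading therefore cannot both be followed without a step that the SAP does not state. Two programmers working independently, one from the note and one from the heading, would produce tables that differ by a factor of 100.

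The table belongs to the safety analysis. Safety and tolerability are the primary objective, and the panel for renal tubular injury is collected at Baseline and on Days 1, 7, 14 and 21. A reader of the study report would take the ng/mg Cr values at face value, for example when comparing them with another source that uses the same unit.

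The treatment of creatinine is a second fault in the same shell. Dividing the normaliser by itself gives rows that carry no information, and the count of six against seven names leaves the biomarker list unclear.

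**Working it through.** **Inputs.** Measured unit ng/mL and normalised unit ng/mg Cr (column headings, Table 14.3.5.4.1 shell); divisor unit mg/dL (note to the same table); division rule (SAP 9.7 and the note); parameter list (SAP 9.7 and the programming note); decimals (shell and programming note).

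**1. Unit factor.** 1 mg/dL = 0.01 mg/mL. For a marker at x ng/mL and creatinine at c mg/dL:

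- rule as written: x / c
- value in ng/mg Cr: x / (0.01 × c) = 100 × x / c

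The SAP gives no concentrations, so the pairs below are assumed for illustration. The ratio does not depend on them.

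| x (ng/mL) | c (mg/dL) | x / c as written | 100 × x / c in ng/mg Cr | ratio |
|---|---|---|---|---|
| 1 | 100 | 0.01 | 1.0 | 100 |
| 50 | 80 | 0.625 | 62.5 | 100 |
| 250 | 200 | 1.25 | 125 | 100 |

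**2. Effect of the fixed decimals.** On the literal rule, a mean or median prints as 0.0 when x / c is below 0.05, which is a true value below 5 ng/mg Cr. A minimum or maximum prints as 0 when x / c is below 0.5, which is a true value below 50 ng/mg Cr. In those cells information is lost, and multiplying the printed table by 100 would not recover it.

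**3. Fold change.** Take the assumed pair 50 ng/mL and 80 mg/dL at baseline, and 90 ng/mL and 120 mg/dL at a later visit.

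- as written: (90/120) / (50/80) = 0.75 / 0.625 = 1.2
- with the factor: 75 / 62.5 = 1.2

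The factor cancels, so fold changes are correct either way.

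**4. Creatinine divided by itself.** With numerator and denominator in the same unit, uCr / uCr = 1 for every subject and visit. If the ng/mL heading is taken at its word, c mg/dL is 10,000 × c ng/mL, and dividing by c gives 10,000 for every subject and visit. In both cases the normalised value is constant, its SD is 0, and the fold change is always 1.

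**5. Count.** Seven analytes are named. Without uCr, six remain: uCLU, uCysC, uKIM-1, uNAG, uNGAL and uOPN. That matches the count stated in SAP 9.7.

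**The case against.** The strongest reply is that the required output unit is explicit in the heading, so the mg/dL in the note can be read as the unit in which creatinine is reported, leaving a competent programmer to convert. SAP 9.7 gives the division with no units and is dimensionally sound. This has force: wrong output is not certain. What remains is that the only rule giving a unit for the divisor is incompatible with the label, and no visible text tells anyone to convert.

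A second reply is that little depends on these rows. The primary endpoint is treatment-emergent adverse events, the panel is not used for eligibility, and the one threshold shown (1.18, in the programming note to Figure 14.5) belongs to the composite, not to absolute levels. That stands, and it limits the consequence to the descriptive summaries of normalised concentration.

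A third reply is that uCr appears in the shell only as the first entry of a generic template, and that a fold-change row fixed at 1 would be noticed. That is plausible, but the programming note repeats uCr in the list of parameters to be run.

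Finally, a flat factor of 100 for all markers relies on the generic ng/mL heading. That heading does not fit creatinine, whose unit the note gives as mg/dL, and no visible text gives a reporting unit for each marker. This objection is accepted and is reflected in the fix.

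**Conclusion.** The point holds as a contradiction within the SAP and should be corrected. Applied literally, the note makes the absolute normalised summaries in Table 14.3.5.4.1 100 times too low for their ng/mg Cr label, and some small values would print as 0. This assumes that the note is coded as written and that the marker is reported in ng/mL. Fold changes, and any composite built only from fold changes, are not affected. Separately, uCr is listed among the biomarkers although it is the divisor; its normalised and fold-change rows are constant by construction, and its measured heading is in the wrong unit.

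A reader might go further and infer that uCr enters the geometric mean composite as a seventh component, so that a constant 1 would pull the composite down against the 1.18 threshold and blunt a renal signal. The documents do not support that. The visible text contains no composite formula, the surrounding text is redacted, and the stated count of six, which is exactly the list without uCr, points the other way. No dilution of the composite is claimed here.

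**What to change.** 1. In the note to Table 14.3.5.4.1, convert creatinine to mg/mL before dividing. For markers reported in ng/mL this is the same as 100 × (ng/mL) / (mg/dL), giving ng/mg Cr. State the reporting unit and the conversion for any marker reported in another unit. Put the same definition in SAP 9.7.
2. Show uCr as a measured value only, in mg/dL, and remove it from the normalised and fold-change parameters in the shell and the programming note.
3. In SAP 9.7, list the six remaining markers as the biomarkers and name uCr separately as the normaliser, so that the list matches the stated count.
4. Use one name, creatinine, for the analyte throughout.

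The cost is a correction to SAP text and one table shell. No data collection, endpoint or fold-change calculation changes.
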